For example, to assess the effects of memantine on "gating" measures in schizophrenia patients, the primary measure will be evaluated by 2-way repeated-measure ANOVA of PPI with memantine dose and prepulse interval as within-subject factors. The hypothesis that memantine will increase PPI in schizophrenia patients will be confirmed by a significant effect of dose (active > PBO) or significant dose x interval (int) interaction and post-hoc comparisons at one or more prepulse intervals. Existing data (see above) provide a strong *a priori* prediction that the 120 ms prepulse interval will be most sensitive to PPI-enhancing effects of MEM. The effect size (d) for PPI-enhancement by 20 mg memantine in HCS was 0.91; with a similar "d" in patients, 30 patients/dose yields power of 0.92 to detect the predicted memantine effects; with maximum expected attrition (n=24), power is 0.85. Past findings also lead to the prediction that these MEM effects would be most robust in subjects exhibiting the lowest basal PPI levels (d=1.80). Using a median split of mean basal (screening) PPI levels, ANOVA as above will detect a significant interaction of memantine dose x basal PPI level, or dose x basal level x int, and significant post-hoc comparisons at one or more prepulse intervals (again, 120 ms being the strongest *a priori* candidate). Given the published "d" in control subjects, a comparable "d" in the proposed 12-15 "low PPI" patients/dose group would yield power >0.95 to detect the predicted memantine effects.

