Lastly, based on the impact of basal PPI level and personality measures in controls, we hypothesize that a critical moderating factor underlying PPI memantine sensitivity is COMT Val158Met genotype; specifically, we predict that “Val/Val” individuals will be most sensitive to memantine-enhanced PPI. This will be tested in two ways: first, by ANOVA as above, with COMT status as a between-subject factor, and memantine dose and prepulse interval as within-subject factors. Significant genotype x dose or genotype x dose x int interactions, with appropriate post-hoc comparisons, would confirm the hypothesis. Estimating $d=1.53$, based on the mean “d” of two “COMT phenotypes” in controls – low basal PPI ($d=1.80$) and high “novelty seeking” personality ($d=1.27$) - the proposed 11 Val/Val and 7 Met/Met patients/dose group would yield power of 0.90 to detect genotype-sensitive memantine effects. It is possible that various factors (including a skewed distribution of allele frequencies, or substantial genotype effects on basal PPI levels) might preclude detection of a significant 2- or 3-way interaction. A secondary (albeit weaker) test of the hypothesis will utilize separate ANOVAs in Val/Val vs. Met/Met subgroups, with predicted PPI-enhancing effects of memantine in the Val/Val but not Met/Met subgroups. Previous reports also predict a significant main effect of genotype, with PPI levels following the Met/Met>Val/Met>Val/Val gradient. Logistic regressions might be used, with genotype coded to reflect “dose” of the Met allele (Val/Val=0, Val/Met=1, and Met/Met=2), to assess the distribution of the neurophysiological and neurocognitive measures. All analyses will be conducted independently for each dose group. If comparable effects are evident with 10 and 20 mg doses, dose groups may be pooled to increase power for exploratory analyses (e.g. to detect genotype x drug effects).

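### The fallback COMT test (a memantine effect in Val/Val but not in Met/Met) does not compare the genotypes, and would appear in about a third of trials with no genotype difference

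*Protocol*

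**What the plan says.** Protocol section 9.j (Statistics) tests the COMT hypothesis in two ways. The first is a mixed ANOVA with genotype between subjects and drug and prepulse interval within subjects: "Significant genotype x dose or genotype x dose x int interactions, with appropriate post-hoc comparisons, would confirm the hypothesis". (The factor called dose is active drug against placebo.) The protocol then concedes that skewed allele frequencies or genotype effects on basal PPI "might preclude detection of a significant 2- or 3-way interaction", and adds: "A secondary (albeit weaker) test of the hypothesis will utilize separate ANOVAs". In full, the fallback is "separate ANOVAs in Val/Val vs. Met/Met subgroups, with predicted PPI-enhancing effects of memantine in the Val/Val but not Met/Met subgroups".

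The sizes are "the proposed 11 Val/Val and 7 Met/Met patients/dose group", and "All analyses will be conducted independently for each dose group", so 11 and 7 are the numbers in each subgroup ANOVA. Alpha is 0.05. The planning effect for the overall drug hypothesis is given earlier in 9.j: "The effect size (d) for PPI-enhancement by 20 mg memantine in HCS was 0.91".

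The SAP lists drug, dose, diagnosis and prepulse interval for PPI. It does not mention genotype, so the protocol holds the only stated rule for COMT.

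**The concern.** The moderation hypothesis is that the drug effect differs between genotypes. Two separate within-genotype tests, one significant and one not, do not estimate or test that difference. Calling the approach weaker suggests lower sensitivity. The actual fault is that the difference is left untested and the rate of false support is not held at 0.05. That rate depends on how large the common drug effect is and on the power of two small, unequal subgroups.

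The main PPI hypothesis is that memantine works. If it works equally in everyone, the larger Val/Val group is more likely to reach significance simply because it is larger. The fallback is also introduced for the case where the interaction is not detected, so it can supply support after the valid test has failed. The protocol's progress report hopes to use markers, including Val/Val, to pick out patients likely to respond. A false finding here would point to the wrong group.

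**Working it through.** **Inputs from protocol 9.j:** alpha 0.05; 11 Val/Val and 7 Met/Met per dose group; d = 0.91, with stated power 0.92 at n = 30 and 0.85 at n = 24; drug as a within-subject factor. **Input from the SAP:** five prepulse intervals.

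**Assumptions:** the same standardised change-score effect (dz) in both genotypes; two-sided tests; drug main effect only, except in the sensitivity analysis.

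**Step 1: scale of the planning effect.** The protocol does not say how d is scaled. The paired-test power is P(|t′| > t(0.975, n−1)), where t′ is noncentral t with n−1 df and noncentrality dz·√n.

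| dz | n = 30 | n = 24 |
|---|---|---|
| Protocol states | 0.92 | 0.85 |
| 0.64 (= 0.91/√2) | 0.923 | 0.851 |
| 0.91 | 0.998 | 0.989 |

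Solving the stated powers for dz gives 0.636 and 0.639. The value 0.64 therefore reproduces the protocol's planning. The value 0.91 does not, and is kept as the upper reading.

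**Step 2: probability of the predicted pattern with no genotype difference.** The subgroups are independent, so

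P(pattern) = P(Val/Val significant, active > placebo; n = 11) × [1 − P(Met/Met significant; n = 7)].

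- dz 0.64: 0.483 × (1 − 0.298) = 0.483 × 0.702 = 0.339
- dz 0.91: 0.776 × (1 − 0.524) = 0.776 × 0.476 = 0.370

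Over a wider range of dz:

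| dz | 0 | 0.2 | 0.3 | 0.4 | 0.64 | 0.8 | 0.91 | 1.27 | 1.53 |
|---|---|---|---|---|---|---|---|---|---|
| P(pattern) | 0.024 | 0.08 | 0.13 | 0.19 | 0.34 | 0.38 | 0.37 | 0.19 | 0.08 |

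The maximum is 0.38, near dz 0.8. The reverse pattern (Met/Met only) occurs in 0.154 of trials at dz 0.64 and 0.117 at 0.91, so the unequal sizes favour the predicted direction.

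**Step 3: comparator.** One two-sided interaction test has error 0.05 (0.025 in the predicted direction). The protocol accepts either of two, unadjusted: 1 − 0.95² = 0.0975, and simulation gives 0.097. This ignores the required post-hoc step, which would lower it. Uncorrected non-sphericity over the five intervals raised it to about 0.11 to 0.13 in simulation.

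**Step 4: pattern when the interaction test has failed.** This used 200,000 simulated trials, five intervals, correlation 0.5 and a flat effect. Figures are shares of all trials.

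| | dz 0.64 | dz 0.91 |
|---|---|---|
| Pattern, genotype × drug not significant | 0.316 | 0.346 |
| Pattern, neither interaction significant | 0.300 | 0.329 |

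Adding the roughly 0.10 from the interaction rule, some form of support appears in about 0.40 (0.300 + 0.097) to 0.43 (0.329 + 0.097) of trials with no moderation.

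**Step 5: sensitivity.**

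- *Interval profile.* For the overall hypothesis, 9.j says it "will be confirmed by a significant effect of dose (active > PBO) or significant dose x interval (int) interaction". If the same rule decides significance within each subgroup (post-hoc step not modelled), dz 0.64 to 0.91 gives 0.34 to 0.36 for a flat effect, 0.18 to 0.36 for one rising toward 120 ms, and 0.00 to 0.20 for one strongly concentrated there. At dz 0.4 the range over the same profiles is 0.21 to 0.36.
- *Subgroup sizes, at dz 0.64 and 0.91.* Equal groups of 9 and 9 give 0.24 and 0.22. If attrition left 9 and 6 (an assumption), the rates would be 0.30 and 0.38.

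**The case against.** The protocol ranks its own tests. It reserves the language of confirmation for the interaction and labels the subgroup ANOVAs secondary and weaker; nothing says that the subgroup pattern overrides a null interaction. That is correct, and it limits the severity. But the fallback is still called a test of the hypothesis, and it is introduced for the case where the interaction is not found. The protocol does not say that the pattern is only descriptive.

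The headline rate is also conditional. The planning effect lies near the peak of the curve, and only dz 0.64 agrees with the stated power, so 34% is the better supported end. No PPI effect size is given for 10 mg, although each dose group is analysed separately. The protocol expects 120 ms to be the most sensitive interval; if the effect is strongly concentrated there and a drug-by-interval effect counts within a subgroup, the rate can fall to between 0 and 0.20, because Met/Met also tends to become significant. The realised genotype split may differ from 11 and 7 and move the rate either way. The two-genotype calculation leaves out about 12 Val/Met patients per dose group (30 − 18), but including them barely changes it. All this stands as a limit on the exact percentage. It does not rescue the method: a false-support rate that moves with the common drug effect and the subgroup sizes shows that the procedure is not testing moderation.

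Last, COMT lies outside the SAP's stated primary hypothesis. That makes this a secondary matter, but nothing in the SAP withdraws the protocol's rule.

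**Conclusion.** The concern holds. The separate ANOVAs do not test whether memantine acts differently in Val/Val and Met/Met patients. With equal effects in both, 11 and 7 patients, two-sided 0.05 and a drug main effect only, the predicted pattern appears in about 34% of trials at the effect that reproduces the protocol's power, and in 37% at the upper reading of d. The protocol's either-interaction rule gives about 10%, and a single interaction test 5%. Smaller or much larger true effects, equal subgroups, or an effect confined to the longest interval lower the rate. This should be corrected. It does not affect the primary PPI hypothesis, but it is a prespecified route to a false claim about which patients respond.

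**What to change.** Remove the separate ANOVAs as a test of moderation. Base any claim on the genotype × drug interaction. If genotype × drug × interval is to count as well, either name one of the two as the confirming test or split alpha: at 0.025 each, the either-interaction rate falls from about 0.10 to 0.05 (1 − 0.975² = 0.049). Report the Val/Val and Met/Met effects with 95% confidence intervals as description only, and report a non-significant interaction as inconclusive.

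The cost is wording; neither data nor sample size changes. The interaction estimate stays imprecise: its 95% confidence interval half-width is t(0.975, 16) × √(1/11 + 1/7) = 2.12 × 0.483 = 1.02 SD of the change score. Naming one interaction costs that test no power. Splitting alpha lowers genotype × drug power from 0.84 to 0.75, if the stated d = 1.53 is read as the between-genotype difference in change-score SDs (an assumption; two-sample noncentral t, 11 and 7 patients).

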The proposed study samples (Table 3) reflect both logistical and power consideration (see above, section "8. j. Statistics.") that differ across the several different studies covered by this application. Testing in the "ONE-DAY" session is designed for parametric "mini-studies", and the proposed sample of "up to 50 subjects" per year will allow us to study up to 5 different sets of stimulus parameters, with n's of 10 subjects per study. To study drug effects on PPI in normal control subjects, our target samples have historically been 20-30 subjects per dose; however, with the addition of COMT subgroup analyses, we currently plan to test 120 subjects in the within-subject amphetamine study, over a 2 year period (n=60/year). To study the effects of memantine on PPI and related measures in schizophrenia patients, we are proposing to study a total of 60 subjects: 30 per dose (10 and 20 mg). As this testing will be conducted over 2 - 3 years, we estimate recruitment needs of approximately 2 subjects per month, which will be easily accommodated by our recruitment capacity at the UCSD Medical Center, based on experience over the past 25 years.

Records and data will be rigorously protected, as described below. Aside from historical and questionnaire data, startle response, negative priming, MCCB, mismatch negativity and gamma band synchronization data will be obtained. Urine will be obtained for toxicological analysis as part of the subject exclusion process. Blood samples will be collected to identify genes that may be associated with PPI or its sensitivity to drugs.

The ethnic population in our male studies from the last 5 years (as we've only studied males exclusively based on drug study exclusion criteria) and is expected in the following years are:

Asian/Pacific Islander	29%
Black (not Hispanic)	3%
Hispanic	10%
White (not Hispanic)	56%
Other/unknown	2%

The ethnic population in our non-drug female studies from the last 5 years and is expected in the following years are:

Asian/Pacific Islander	12.5%
Black (not Hispanic)	2.5%
Hispanic	8.75%
White (not Hispanic)	72.5%
Other/unknown	3.75%

These numbers reflect the location of where we typically recruit subjects.

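### The predicted COMT gradient in PPI is to be read from a genotype main effect that averages placebo and memantine days, where the plan's own predicted genotype-by-drug interaction attenuates it and may cancel or reverse it

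*Protocol*

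**What the plan says.** The COMT plan for the schizophrenia memantine study is one paragraph of Protocol section 9, part j (Statistics). Its hypothesis is that Val/Val "individuals will be most sensitive to memantine-enhanced PPI". The main test is an ANOVA "with COMT status as a between-subject factor, and memantine dose and prepulse interval as within-subject factors", and significant genotype-by-dose or genotype-by-dose-by-interval terms would confirm the hypothesis. A weaker, secondary test runs separate ANOVAs by genotype, "with predicted PPI-enhancing effects of memantine in the Val/Val but not Met/Met subgroups".

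The paragraph then adds the prediction at issue: "Previous reports also predict a significant main effect of genotype, with PPI levels following the Met/Met>Val/Met>Val/Val gradient". It gives no effect size, power or decision rule for it. It mentions a possible regression on Met-allele count (0, 1, 2), without limiting it to drug-free data. It also says: "All analyses will be conducted independently for each dose group". Pooling the doses is optional, exploratory and conditional on similar effects at 10 and 20 mg.

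The paragraph recognises that genotype differences in basal PPI could hide the interaction. It does not consider the reverse. The SAP does not mention genotype.

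**The concern.** The two predictions pull against each other in the statistic chosen for one of them. Val/Val is predicted to have the lowest PPI and also to be the group that memantine raises. A main effect that includes the memantine day therefore mixes the drug-free gradient with a drug effect acting the other way.

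The target is a drug-free quantity. Protocol section 7 describes the earlier genotype findings as differences in basal PPI, and section 9.j uses the known effect of COMT on PPI level to support its working-memory prediction. If the moderator hypothesis is true, a null or reversed main effect could come from the averaging and be mistaken for failure to replicate.

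Splitting by dose adds a second, avoidable loss. Placebo-day PPI does not depend on whether the active pill is 10 or 20 mg.

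**Working it through.** **Inputs from Protocol section 9.j.** Alpha 0.05 (taken as two-sided). 11 Val/Val and 7 Met/Met per dose group. Effect size: "Estimating $d=1.53$, based on the mean" of 1.80 and 1.27; (1.80 + 1.27)/2 = 1.535.

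**The plan's own figure.** It says "the proposed 11 Val/Val and 7 Met/Met patients/dose group would yield power of 0.90 to detect genotype-sensitive memantine effects". With d = 1.53 the noncentrality is 1.53 × √(11×7/18) = 1.53 × 2.068 = 3.16. The two-sided normal approximation gives Φ(3.16 − 1.96) = 0.886, close to the stated 0.90; a two-sided t test gives 0.844. This figure is for the interaction. None is stated for the genotype main effect.

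**Assumptions.** Each day's PPI has SD 1. The drug-free gap, Met/Met minus Val/Val, is b, varied from 0.5 to 1.53. The day-to-day correlation r is 0.5 to 0.9. The interaction D is the Val/Val gain minus the Met/Met gain, with the full d placed in Val/Val and none in Met/Met. Because the unit of d is not stated, D is taken two ways:

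- raw SD: D = 1.53
- change-score SD: D = 1.53 × √(2(1−r)), which is 1.53, 1.19 and 0.68 at r = 0.5, 0.7 and 0.9

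**Formulas.** The gap is b on the placebo day and b − D on the active day, so the averaged gap is b − D/2. The SD of a two-day mean is √((1+r)/2). Power is from the noncentral t distribution (16 df for 11 v 7; 34 df for 22 v 14).

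**Example, b = 1.0 and r = 0.7.** Raw unit: gap 1.0 − 0.765 = 0.235; SD √0.85 = 0.922; standardised gap 0.255; power 0.08. Change-score unit: gap 1.0 − 1.185/2 = 0.407; standardised 0.442; power 0.14.

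**Results over r = 0.5 to 0.9 and both units of d (two-sided power).**

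| Drug-free gap b (SD) | Averaged main effect, 11 v 7 | Placebo day, 11 v 7 | Placebo day, both dose groups, 22 v 14 |
|---|---|---|---|
| 0.5 | 0.05–0.09 | 0.16 | 0.30 |
| 0.8 | 0.05–0.15 | 0.34 | 0.62 |
| 1.0 | 0.08–0.26 | 0.49 | 0.81 |
| 1.27 | 0.17–0.46 | 0.69 | 0.95 |
| 1.53 | 0.33–0.66 | 0.84 | 0.99 |

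At b = 0.5 the averaged gap runs from −0.27 to +0.16 SD, so much of that small power is for the wrong direction.

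**Where cancellation falls.** b − D/2 = 0 requires D = 2b. With D = 1.53 that is b = 0.765; with the change-score values 1.19 and 0.68 it is about 0.59 and 0.34.

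**If there is no interaction.** Averaging two days helps slightly: at b = 1.0 and 11 v 7, power is 0.51 to 0.61, against 0.49 on the placebo day alone.

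**The case against.** A reader might infer that the interaction cancels the gradient outright. The documents do not support that. Cancellation needs an interaction exactly twice the drug-free gap, and no gap is given. Above that point the gradient shrinks but survives; below it, it reverses.

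The table may also overstate the loss, because it applies the full d at every prepulse interval and in either dose group. Section 9.j expects the strongest effect at 120 ms, and the SAP lists five intervals (10, 20, 30, 60 and 120 ms). Section 9.j ties its control effect size of 0.91 to 20 mg, and section 9.h places the group's experience at the higher of the two proposed doses. If the drug effect is concentrated at some intervals or weaker at 10 mg, less is lost. This objection stands as to size, not direction.

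Nor does the plan say that a null main effect would count as failed replication, or make the gradient a hypothesis test. An interaction large enough to erase the gradient would usually be detected (0.84 by two-sided t, 0.90 as stated) and followed by post-hoc comparisons. That lowers the risk of misreading. It does not remove it, because no placebo-day genotype comparison is named.

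The pooling clause is only a partial answer: it is optional, exploratory and depends on similar drug effects, which have no bearing on a drug-free comparison.

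**Conclusion.** The point holds as a limited one. As written, the genotype main effect is the wrong statistic for the predicted gradient: it includes the memantine day, and the plan's own moderator prediction reduces it by half the interaction. In every scenario calculated with that interaction present, the placebo-day test had more power at the same 11 v 7.

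The size is conditional on an assumed drug-free gap, an assumed day-to-day correlation and an unstated unit for d. The power figures compare Val/Val with Met/Met only, leaving out the Val/Met patients. They show how much may be lost; they do not estimate this trial's power.

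A reader might go further and infer that the primary memantine test or the COMT moderator test is compromised. Neither is: the moderator hypothesis is judged on the interaction terms, and the gradient is a supporting prediction.

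**What to change.** In section 9.j, state that the genotype gradient will be tested on placebo-day PPI in both dose groups together, either with genotype at three levels or with Met-allele count 0/1/2. Keep the dose-group ANOVA for the genotype-by-drug interactions, and say that its genotype main effect is not the test of the gradient.

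Screening PPI is also drug-free and could be added, but only if patients were not selected on it. Section 9.e allows subjects to be invited back on genotype or on upper- versus lower-quartile PPI, and it should be stated whether that applied to the patients.

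The change is a sentence or two and needs no new data. Its one statistical cost is the small noise reduction from averaging two days when there is no interaction (0.49 against 0.51–0.61 at a gap of 1.0 SD, 11 v 7). Combining the dose groups more than recovers it (0.81).

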j. Statistics: Tests for homogeneity of variance are performed, and if appropriate, analyses of variance (ANOVA) used. Statview/Superanova software is used on the Macintosh. For startle data, P-Alone amplitude, PPI and startle latency are analyzed by ANOVAs; for drug studies, drug dose is used as a within-subject factor. Habituation is detected by a significant effect of trial block. Visuospatial priming is analyzed separately for baseline, facilitation, and inhibition conditions using ANOVAs. Baseline is a measure of visuospatial response time, while facilitation and inhibition scores are measures of sensorimotor modulation. Nonparametric statistics are used for the Latent Inhibition analyses because data from this test tend toward a bimodal distribution. A rank sum factorial analysis is used for the data. Other dependent measures will be analyzed with parametric or non-parametric analyses, generally consisting of mixed design ANOVAs, as appropriate. Following a significant ANOVA, specific comparisons are made using Tukey's tests. Alpha is 0.05.

Power considerations: Sample sizes vary across the different studies, based on issues ranging from the study design and goals to empirical evidence for effect sizes with the proposed drug or measure. For example, "ONE-DAY" studies are designed to identify and "pilot" optimal stimulus parameters for testing specific hypotheses, and these studies may not be powered to achieve traditional levels of statistical significance. On the other hand, designing studies of drug effects on PPI and related measures in control or patient populations requires detailed power information.

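### The COMT genotype hypothesis has two unadjusted dose-specific tests, either of which could confirm it, plus an optional pooled analysis whose trigger is undefined and read from the same data

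*Protocol*

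**What the plan says.** In protocol section 9.j (Statistics), schizophrenia patients receive placebo and one active dose, with 30 patients at 10 mg and 30 different patients at 20 mg. Within a dose group, the factor that the protocol calls dose is therefore active drug versus placebo.

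- **Criterion for the moderator hypothesis:** "Significant genotype x dose or genotype x dose x int interactions, with appropriate post-hoc comparisons, would confirm the hypothesis". No dose is named.
- **Fallback:** "A secondary (albeit weaker) test of the hypothesis will utilize separate ANOVAs in Val/Val vs. Met/Met subgroups".
- **Handling of the two doses:** "All analyses will be conducted independently for each dose group".
- **Pooling:** "If comparable effects are evident with 10 and 20 mg doses, dose groups may be pooled to increase power for exploratory analyses". Genotype-by-drug effects are the example given.
- **Error control:** "Following a significant ANOVA, specific comparisons are made using Tukey's tests. Alpha is 0.05". Nothing is said about adjustment across dose groups.
- **Power:** "the proposed 11 Val/Val and 7 Met/Met patients/dose group would yield power of 0.90 to detect genotype-sensitive memantine effects", using d = 1.53, which is "based on the mean “d” of two “COMT phenotypes” in controls".

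The SAP makes dose a between-subject factor in the cognition (MCCB) analysis and lists dose among the interacting variables for PPI. It does not mention genotype or pooling. It is written after the fact and states conclusions for both main drug hypotheses.

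**The concern.** The same genotype-by-drug question is asked in two independent patient groups at 0.05 each, and a positive answer in either could be presented as confirmation. That alone roughly doubles the nominal error rate.

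The pooled analysis adds a second problem. Whether it is done depends on a judgement of similarity made on the data that are then pooled, with no test, margin or decision-maker stated. The most precise estimate of the moderator effect may therefore appear or not according to how the results look.

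The protocol calls COMT genotype a critical moderating factor, and identifying biomarker-defined responders is among its stated goals. A loosely specified test here affects one of its main scientific claims.

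**Working it through.** **Inputs.** From section 9.j: alpha 0.05 (sidedness not stated; two-sided assumed); 11 Val/Val and 7 Met/Met per dose; d = 1.53 (PPI) and 1.20 (working memory, WM); d = 0.91 for PPI at 20 mg in healthy subjects; 30 patients per dose, 24 at maximum attrition. Assumptions: d for the genotype contrast is in SDs of the drug-minus-placebo change, and data are normal with common variance.

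**1. The plan's own figure.** The SE of the genotype contrast in one dose group is √(1/11 + 1/7) = 0.483 SD, so 1.53/0.483 = 3.16. The normal approximation gives Φ(3.16 − 1.96) = 0.886, close to the stated 0.90. A one-sided t gives 0.916 and a two-sided t (16 df) gives 0.844. The companion WM figure of 0.65 matches the two-sided t (0.645), not the normal approximation (0.699). The two stated powers do not appear to share one formula.

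**2. Error rate with no genotype effect.**
- Two independent tests: 1 − 0.95² = 0.0975. Simulation (300,000 trials, 11 v 7 per dose): 0.098.
- Adding a pooled 22 v 14 test: 0.117 if always done, 0.116 if done only when the 30 v 30 dose difference is non-significant. The increment is about 2 points because the pooled test reuses the same data. Three independent tests would give 0.143.
- The pooled test on its own, given pooling: 0.050 if the trigger is a non-significant dose difference; 0.098 if the trigger is only that the two genotype effects share a sign. The second follows because about half of null trials agree in sign and pooled significance arises almost only in those: 0.05/0.5 ≈ 0.10.

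These counts leave out the second qualifying interaction (with prepulse interval) and the subgroup ANOVAs.

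**3. Can the doses be told apart?** The SE of the difference in mean change is √(2/30) = 0.258 SD, and the 95% half-width is 2.00 × 0.258 = 0.52 SD.

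Power depends on the scale of 0.91. Taken as SDs of change, a paired test gives 0.998 (n = 30) and 0.989 (n = 24), against the stated 0.92 and 0.85. Taking 0.91/√2 = 0.64 gives 0.92 and 0.85, matching both. The 0.64 scale is inferred, so both are shown:

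| True 10 mg effect | Power, 0.64 scale | Power, 0.91 scale |
|---|---|---|
| None | 0.68 | 0.93 |
| Half of 20 mg | 0.23 | 0.41 |

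For the genotype contrast itself (18 homozygotes per dose), the SE of the between-dose difference is √2 × 0.483 = 0.684. Power is 0.58 if the full 1.53 exists at one dose only, and 0.19 for a difference of 0.765.

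**4. One model with all interactions.** The dose-averaged genotype-by-drug contrast has SE 0.684/2 = 0.342. Its power at two-sided 0.05 (32 df, homozygotes only) is:

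| True genotype effect at 10 mg | Average d (PPI, WM) | Power PPI | Power WM |
|---|---|---|---|
| Same as 20 mg | 1.53, 1.20 | 0.99 | 0.93 |
| Half | 1.15, 0.90 | 0.90 | 0.72 |
| None | 0.765, 0.60 | 0.58 | 0.40 |

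Dose-specific power for PPI moves from 0.844 to 0.866 when error df go from 16 to 32, or from 0.862 to 0.874 if Val/Met patients are kept in the model (27 to 54 df).

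**The case against.** A reader might infer that the plan offers three equal chances to confirm the hypothesis. The text does not support that. Pooling is permissive and labelled exploratory; only the per-dose interactions are said to confirm. Pooling adds about 2 points, and the bulk of the inflation comes from the two unadjusted tests. Nor is three the plan's own count, since each dose group has two qualifying interactions plus the subgroup ANOVAs.

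A reader might also infer that 30 patients per dose can never distinguish the doses. That is too strong: an inert 10 mg dose would be detected with power 0.68 to 0.93, depending on the effect-size scale. What stands is that a half-size effect would usually be missed, so a lack of visible difference is weak evidence that the doses act alike.

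The loss of error degrees of freedom from separate fits is real but worth only 1 to 3 points of power. It is not a reason for change by itself.

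It is also fair that this is a moderator hypothesis, separate from the main PPI test, and that the SAP already treats dose as a model factor for the main drug hypotheses. But the SAP gives no rule for the genotype test, so it does not settle the matter.

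**Conclusion.** The point holds, centred on the two unadjusted dose-specific tests. As written, the chance of a false claim of genotype moderation at one dose or the other is about 9.8%, rising to about 11.7% if a pooled result is also put forward, against 5% for one named test. Neither figure is the plan's full error rate, because other routes to a positive result are not counted. The pooling trigger is undefined, and under a same-direction reading the pooled test alone runs at about 9.8%.

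The error rates rest on normal data, two-sided tests and the 11 and 7 homozygote counts. The dose-separation powers rest on an unstated effect-size scale and an unknown 10 mg effect, hence the ranges. The protocol's separate analyses and the SAP's dose-as-factor model also differ and need to be reconciled. This should be corrected, but it does not touch the main PPI test of drug against placebo.

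**What to change.** Replace the separate-analysis and pooling sentences with one model in all patients: drug, dose group, genotype and their interactions. This agrees with the SAP's use of dose as a factor. Then:

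- Name one genotype-by-drug contrast as the test of the hypothesis. As a statistical choice, the 20 mg contrast is the natural one: the main-effect sizes (0.91 for PPI, 0.73 for WM) are stated for 20 mg, and the protocol says that the group's experience of the two trial doses is limited to it.
- State whether the contrast is taken at 120 ms or averaged over prepulse intervals, and how Val/Met patients enter.
- Always report the 10 mg contrast, the 10-versus-20 mg contrast and the dose-averaged contrast with confidence intervals, as supportive. Make no pooling decision from the data.
- Add the genotype analysis to the SAP, or say that it was not done.

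**Cost.** No extra patients or visits. A common error variance across dose groups is assumed, and a genotype effect present only at 10 mg could no longer confirm the hypothesis. If both doses must be able to confirm, testing each at 0.025 controls the error but lowers PPI power from 0.844 to 0.749 (two-sided t).

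Because the SAP already reports results, this cannot simply be written in as prespecified. Any choice of contrast made after seeing the data should be labelled post hoc, with all dose-specific and dose-averaged contrasts shown.
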